6.5. Multiplicity Adjustment

Multiplicity arising from testing of secondary endpoints will be addressed by using a fixed sequence hierarchical testing procedure. A step-down testing procedure will be applied where inference for an endpoint in the predefined hierarchy is dependent on statistical significance having been achieved for the previous endpoints in the hierarchy.

The hierarchy of endpoints is defined as follows:

- Primary endpoint
- Key secondary endpoint 1
- Key secondary endpoint 2
- Key secondary endpoint 3

All the tests will be performed at the 0.05 level of significance following the pre-specified order. The testing of the first key secondary endpoint will be conducted if the result of the primary

endpoint is statistically significant and testing of the second key secondary endpoint will be conducted if the result of the first key secondary endpoint is statistically significant and so on.

The other secondary endpoints and exploratory endpoints do not fall under this hierarchical approach as no multiplicity adjustment will be made for such endpoints and only nominal p-values will be reported.

6.6. Interim Analyses

No interim analyses will be conducted for this study.

Data Safety Monitoring Board (DSMB) will be set up for the study who will review safety data to mitigate the risk. Safety monitoring will occur throughout the study to assess the risks of treatment.

A DSMB charter will be written. This charter will include the list of tables and listings to be generated for the DSMB review.

6.7. Stopping Rules for the study

During the conduct of the study, AEs and SAEs will be reported (Protocol Section 9.3.1). These events are continuously reviewed by the medical monitor at the frequency established in the medical monitoring plan.

The sponsor may decide to stop enrollment early due to recommendations from the external, independent DSMB (protocol section 11.1.4). The DSMB will meet at an appropriate frequency, as described in the DSMB charter. The DSMB will also convene if $\geq 3\%$ of study participants have developed a TEAE of CTCAE \geq Grade 3 due to serious injuries to the foot caused by the local complications of the injection or if $\geq 3\%$ of study participants have experienced anaphylaxis after the study treatment. In that setting, the DSMB will conduct an independent assessment and make a recommendation regarding study continuation based upon their overall assessment of risks and benefits to study participants based upon a review of unblinded data.

This study may be terminated by the sponsor for any reason at any time. This can include new safety concerns that can invalidate the earlier positive risk-benefit assessment.

6.8. Treatment Group

All summary tables related to ITT and Safety Population, except study intervention exposure will be presented by treatment group (“EN3835” “Placebo”) and Overall.

All efficacy analyses related to ITT population, FAS and mITT population will be presented by treatment group (“EN3835” “Placebo”).

7. STATISTICAL ANALYSES

7.1. Participant Disposition

The number of participants included in each study population will be summarized by treatment group and overall (if applicable). Participants excluded from the Safety Population, ITT Population, FAS and mITT Population will be listed.

The number and percentage of participants screened, randomized, completed, and withdrawn from the study, as well as the primary reason for withdrawal from the study will be summarized by treatment group and overall (if applicable).

A separate listing of disposition data, participants discontinued from study, and screen failure including the reasons for screen failure will be provided. In addition, a listing for exclusion from analysis populations will be provided.

7.2. Protocol Deviations

Protocol deviations will be summarized by deviation classification (important/not important), by treatment group and overall (if applicable).

A separate listing of all protocol deviations for each visit will be presented by participant.

7.3. Demographics and Baseline Characteristics

The demographic and baseline characteristics will be summarized using the Safety Population, ITT Population and FAS, by treatment group, and overall.

Separate listings by population will be provided if these populations are not identical to the Safety Population.

7.4. Medical and Surgical History

Medical history will be coded using MedDRA. Medical and surgical history data will not be summarized; however, a listing will be provided by participant using the Safety Population.

A separate listing for plantar fibromatosis history will also be provided by participant using the Safety Population.

7.5. Prior/Concomitant Medications and Procedures

Prior and concomitant medications will be summarized by treatment group and overall (if applicable) using frequency and percentages by active ingredient within each ATC, with ATC and active ingredients ordered alphabetically. Prior and concomitant non-drug therapies (procedures) will be summarized by treatment group and overall (if applicable) using frequency and percentages with name of the procedures ordered alphabetically. Multiple use of the same medication/procedure by a participant will be counted only once.

A participant listing indicating prior and concomitant medications and procedures will be provided. Similarly, a separate listing of medications and procedures for plantar fibromatosis will also be presented by participant.

The prior and concomitant medications and procedures will be summarized and listed using the Safety Population.

7.6. Efficacy Analyses

For the primary and key secondary efficacy endpoints, ITT Population will be the primary analysis population. Supportive efficacy analyses will also be performed using FAS and mITT Population. If the difference between FAS and mITT is no more than 5 participants, supportive analyses using FAS will not be generated. All the efficacy listing will be provided by ITT population.

For the data collected at nodule level, analyses will be performed at participant level and nodule level.

Table 27: List of Analyses Performed on All Efficacy Endpoints

Endpoint (Primary/ Secondary /Exploratory)	Endpoint	Primary analyses	Subgroup Analyses	Sensitivity Analyses	Supportive Analyses
Primary	The difference between EN3835 and placebo in the mean change from Baseline (Day 1) to Day 57 on the foot pain subscale (total score on 9 items) of the FFI ranging from 0 (“None”) to 4 (“Extreme”).	ANCOVA (ITT)	ANCOVA (ITT)	
 • MMRM based on (Observed Data) (ITT) • MMRM based on TPA (ITT) 	
 • ANCOVA (FAS) • ANCOVA (mITT)
1 st Key Secondary	The difference between EN3835 and placebo in the mean change from Baseline (Day 1) to Day 57 on the total score of the FFI pain and difficulty subscales (combined).	ANCOVA (ITT)	ANCOVA (ITT)	
 • MMRM based on (Observed Data) (ITT) • MMRM based on TPA (ITT) 	
 • ANCOVA (FAS) • ANCOVA (mITT)
2 nd Key Secondary	The difference in the proportion of EN3835-treated participants and those receiving only placebo reporting “Minimally Improved” (+1) “Much Improved” (+2) or “Very Much Improved” (+3) on the Clinician Global Impression of Change Scale, a 7-point scale ranging from –3 (“Very Much Worse”) to +3 (“Very Much Improvement”) at Day 57.	Cochran-Mantel-Haenszel method (ITT)	Cochran-Mantel-Haenszel method (ITT)	Cochran-Mantel-Haenszel based on TPA (ITT)	
 • Cochran-Mantel-Haenszel method (FAS) • Cochran-Mantel-Haenszel method (mITT)

Table 27: List of Analyses Performed on All Efficacy Endpoints (Continued)

Endpoint (Primary/ Secondary /Exploratory)	Endpoint	Primary analyses	Subgroup Analyses	Sensitivity Analyses	Supportive Analyses
3 rd Key Secondary	The difference between EN3835 and placebo in the mean change from Baseline (Day 1) to the Day 57 in the nodular hardness of the treated nodules by durometer measurements.	ANCOVA (ITT)-Participant level analyses	ANCOVA (ITT)-Participant level analyses	
 • MMRM based on (Observed Data) (ITT) • MMRM based on TPA (ITT) 	
 • ANCOVA (FAS) • ANCOVA (mITT) • Nodule level analyses - MMRM (Observed Data) (ITT) • Nodule level analyses - MMRM (TPA) (ITT)
Secondary	The mean change from Baseline (Day 1) to Days 15, 29, 43, and 57 on the pain subscale of the FFI (total score on 9 items), ranging from 0 (“None”) to 4 (“Extreme”) with EN3835 vs placebo.	MMRM based on (Observed Data) (mITT)			
Secondary	The mean change from Baseline (Day 1) to Days 15, 29, 43, and 57 on the total combined score of the pain and difficulty subscales of the FFI with EN3835 vs placebo.	MMRM based on (Observed Data) (mITT)			
Secondary	The difference in the proportion of EN3835-treated participants and those receiving only placebo reporting “Minimally Improved” (+1) “Much Improved” (+2) or “Very Much Improved” (+3) on the Clinician Global Impression of Change Scale, a 7-point scale ranging from -3 (“Very Much Worse”) to +3 (“Very Much Improvement”) at Day 15, 29, 43 and 57.	Cochran-Mantel-Haenszel method (mITT)			
Secondary	The mean change from Baseline (Day 1) to Days 15, 29, 43, 57 in the nodular hardness of the treated nodules by durometer measurements with EN3835 vs placebo	MMRM based on (Observed data) (mITT)			Nodule level analyses - MMRM (Observed Data) (mITT)
Exploratory	The difference between EN3835 and placebo in the mean change from Baseline (Day 1) to Days 15, 29, 43, and 57 on the FFI total score of 21 items with the score of each item ranging from 0 to 4, with 4 indicating higher severity.	MMRM based on (Observed data) (mITT)			

Table 27: List of Analyses Performed on All Efficacy Endpoints (Continued)

Endpoint (Primary/ Secondary /Exploratory)	Endpoint	Primary analyses	Subgroup Analyses	Sensitivity Analyses	Supportive Analyses
Exploratory	The difference between EN3835 and placebo at Day 57 on the PGIS PF Overall score at Days 15, 29, 43, and 57 on the PGIS PF Overall score, ranging from 0 (“None”) to 4 (“Severe”).	Wilcoxon rank-sum test & H-L estimator (mITT)			
Exploratory	The difference between EN3835 and placebo at Day 57 on the foot pain subscale of the PGIS at Days 15, 29, 43, and 57 on the PGIS foot pain subscale, ranging from 0 (“None”) to 4 (“Severe”) with EN3835 vs placebo.	Wilcoxon rank-sum test & H-L estimator (mITT)			
Exploratory	The difference between EN3835 and placebo at Day 57 on the difficulty subscale of the PGIS at Days 15, 29, 43, and 57 on the PGIS difficulty subscale, ranging from 0 (“None”) to 4 (“Severe”) with EN3835 vs placebo.	Wilcoxon rank-sum test & H-L estimator (mITT)			
Exploratory	The difference between EN3835 and placebo at Day 57 on the activity limitation subscale of the PGIS at Days 15, 29, 43, and 57 on the PGIS activity limitation subscale, ranging from 0 (“None”) to 4 (“Severe”) with EN3835 vs placebo.	Wilcoxon rank-sum test & H-L estimator (mITT)			
Exploratory	The difference in the proportion of participants treated with EN3835 or placebo reporting Minimal Improvement (+1), Much Improvement (+2), and Very Much Improvement (+3) on the PGIC scale- PF Overall, a 7-point scale ranging from -3 (“Very Much Worse”) to +3 (“Very Much Improvement”) on Days 15, 29, 43, and 57.	Cochran-Mantel-Haenszel method (mITT)			
Exploratory	The difference in the proportion of participants treated with EN3835 or placebo reporting Minimal Improvement (+1), Much Improvement (+2), and Very Much Improvement (+3) on the foot pain subscale of the PGIC scale, a 7-point scale ranging from -3 (“Very Much Worse”) to +3 (“Very Much Improvement”) on Days 15, 29, 43, and 57.	Cochran-Mantel-Haenszel method (mITT)			

Table 27: List of Analyses Performed on All Efficacy Endpoints (Continued)

Endpoint (Primary/ Secondary /Exploratory)	Endpoint	Primary analyses	Subgroup Analyses	Sensitivity Analyses	Supportive Analyses
Exploratory	The difference in the proportion of participants treated with EN3835 or placebo reporting Minimal Improvement (+1), Much Improvement (+2), and Very Much Improvement (+3) on the difficulty subscale of the PGIC scale, a 7-point scale ranging from -3 (“Very Much Worse”) to +3 (“Very Much Improvement”) on Days 15, 29, 43, and 57.	Cochran-Mantel-Haenszel method (mITT)			
Exploratory	The difference in the proportion of participants treated with EN3835 or placebo reporting Minimal Improvement (+1), Much Improvement (+2), and Very Much Improvement (+3) on the activity limitation subscale of the PGIC scale, a 7 point scale ranging from -3 (“Very Much Worse”) to +3 (“Very Much Improvement”) on Days 15, 29, 43, and 57.	Cochran-Mantel-Haenszel method (mITT)			
Exploratory	The difference between EN3835 and placebo in the mean change from Baseline (Day 1) to Day Days 15, 29, 43, and 57 on the Pain Intensity NRS, ranging from 0 (“None”) to 10 (“Worst Pain Imaginable”) with EN3835 vs placebo.	MMRM based on (Observed Data) (mITT)			
Exploratory	The difference in the proportion of participants treated with EN3835 or placebo reporting to be “Satisfied” (+1) and “Very Satisfied” (+2) on the Subject Satisfaction With Treatment Scale, a 5-point scale ranging from -2 (“Very Dissatisfied”) to +2 (“Very Satisfied”) on Days 15, 29, 43, and 57.	Cochran-Mantel-Haenszel method (mITT)			
Exploratory	The difference between EN3835 and placebo in the mean change from Baseline (Day 1) to Day Days 15, 29, 43, and 57 on the activity limitation subscale (total score on 3 items) of the FFI, ranging from 0 (“Never”) to 4 (“Always”).	MMRM based on (Observed Data) (mITT)			
Exploratory	The difference between EN3835 and placebo in the mean change from Baseline (Day 1) to Days 15, 29, 43, and 57 on the difficulty subscale (total score on 9 items) of the FFI, ranging from 0 (“No Difficulty”) to 4 (“A Lot of Difficulty”).	MMRM based on (Observed Data) (mITT)			

Table 27: List of Analyses Performed on All Efficacy Endpoints (Continued)

Endpoint (Primary/ Secondary /Exploratory)	Endpoint	Primary analyses	Subgroup Analyses	Sensitivity Analyses	Supportive Analyses
Exploratory	The difference between EN3835 and placebo in the mean change from Baseline (Day 1) to Days 15, 29, 43, and 57 in the nodule size of the treated nodules by caliper measurements.	MMRM based on (Observed Data) (mITT)			Nodule level analyses - MMRM (Observed Data) (mITT)
Exploratory	The difference between EN3835 and placebo in the change in nodule consistency from Baseline (Day 1) to Days 15, 29, 43, and 57 as determined by the number of participants with a soft or non-palpable consistency at Day 57.	Cochran-Mantel-Haenszel method (mITT)			Nodule level analyses: Cochran-Mantel-Haenszel method (mITT)
Exploratory	The difference between EN3835 and placebo in the mean change from Baseline (Day 1) to Days 15, 29, 43, and 57 on the FFI composite score, with the score of each of the 21 items ranging from 0 to 4, with 4 indicating higher severity.	MMRM based on (Observed Data) (mITT)			

7.6.1. Primary Analyses

7.6.1.1. Mean Change from Baseline to EOS Visit on the Foot Pain Subscale

The primary estimand is defined by the following:

- **The *primary clinical question of interest* is:** In participants with plantar fibromatosis, what is the difference in mean change from Baseline (Day 1) to Day 57 in the total foot pain score (as measured with the FFI pain subscale) between EN3835 and placebo regardless of discontinuation of study intervention?
- **Treatment condition:** Randomized study intervention (EN3835 or placebo)
- **Target Population:** Adult participants with plantar fibromatosis included in the ITT Population.
- **Variable (Endpoint) of interest:** Mean change from baseline (Day 1) to Day 57 in FFI total foot pain subscale score.
- **Treatments being compared:** The mean change from baseline (Day 1) to Day 57 in FFI total foot pain subscale score will be compared between EN3835 and placebo.
- **Intercurrent Event:** The treatment policy strategy will be adopted for the analyses.
 - Any new or change in concomitant treatment will not be adjusted for primary analyses.
 - Early discontinuation from the study is the potential intercurrent event that could occur. If participants do not have FFI total pain subscale score at Day 57 due to early discontinuation, the missing values will be imputed before the analyses

[figure not shown]
using a multiple imputation washout model. In multiple imputation washout model, all participants who are randomized and have a baseline assessment will be considered (Section 7.6.1.2 for details on imputation).

- **Population Level-Summary measure:** Least square mean (LSM) estimate for treatment difference between EN3835 and placebo.
- **Method of Analyses:** The change from Baseline (Day 1) to Day 57 in the total foot pain subscale score will be calculated after the missing data imputation has been performed and will be analyzed using an Analysis of Covariance (ANCOVA) model on each multiply imputed dataset. The model will include the fixed effect of treatment group and FFI pain subscale score at baseline, the maximum of Nodule length/Nodule width, and the total number of nodules as covariates. Treatment effects from these ANCOVA analyses will then be combined using Rubin's Method via the SAS PROC MIANALYZE procedure. The LSM estimate for each treatment, the LSM of treatment difference, their corresponding 95% confidence interval (CI) and associated p-value will be provided (Section 7.6.1.2 for more details on this analyses).
- **Sensitivity analyses to primary endpoint:** The following sensitivity analyses will be performed on primary efficacy endpoint to assess the impact of missing data:
 - A sensitivity analyses will be performed based on all observed data up to Day 57. The change from Baseline (Day 1) to Day 57 will be analyzed using an MMRM (Section 7.6.1.3).
 - Another sensitivity analyses will be performed using MMRM with imputation of missing values for participant who discontinue treatment or who are withdrawn from the study. The imputed missing values will be adjusted using a TPA (Section 7.6.2).
- **Supportive analyses to primary endpoint:** The primary efficacy endpoint will also be analyzed using ANCOVA by FAS and mITT population.

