10. STATISTICAL CONSIDERATIONS AND METHODS

10.1. Sample Size Determination

The primary endpoint is the difference between EN3835 and placebo in the mean change from Baseline (Day 1) to Day 57 on the foot pain subscale (total score on 9 items) of the FFI ranging from 0 ("None") to 4 ("Extreme").

The sample size was estimated based on an interim analysis of the Day 57 data from Study EN3835-105, a dose-finding Phase 1 study. Assuming a difference in the mean change from Baseline to Day 57 in the pain subscale of FFI between EN3835 and placebo of 5.0 with a 10 standard deviation and 85% statistical power using a 2-sided test ($\alpha = 0.05$), 73 participants per treatment group (146 in total) will be needed to detect this difference between the 2 treatment groups. Assuming a dropout rate of 15%, the total sample size will be 172, eighty-six per treatment group for the study.

Participants will be screened to ensure that approximately 172 participants are randomized into 2 treatment groups, an EN3835 group and a placebo group in a 1:1 ratio.

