10.3.1.1.2. Method of Analysis

The primary estimand will be based on the data at Baseline and Day 57. Therefore participants who discontinue study intervention or discontinue from the study will be encouraged to complete the remaining study visits and evaluations, and provide any additional follow-up information as required by the study. In cases where the participants do not have an FFI pain subscale score at Day 57 due to early study discontinuation, the missing values will be imputed before the analysis using a multiple imputation washout model. The details of the model will be specified in the SAP.

After imputation, the changes from Baseline to Day 57 will be analyzed using an ANCOVA model with treatment group as fixed effect, FFI pain subscale at baseline, the nodule size and the number of nodules as covariates. The summary measure, least squares (LS) mean estimate for treatment difference between EN3835 and placebo and their corresponding 95% confidence intervals (CIs) will be reported.

A sensitivity analysis with tipping-point approach will be implemented, the details of this approach will be specified in the SAP. In addition, another sensitivity analysis will be performed based all observed data up to Day 57. The changes from Baseline will be analyzed using a mixed

effect model for repeated measures (MMRM). This MMRM model will include treatment group, study visit, treatment by visit interaction as fixed effects, and the covariates of the baseline score, nodule size and the number of nodules. The repeated measure is the participant visits. The dependent variable will be the change from the Baseline at each visit. The summary measure, LSM estimate for treatment difference at Day 57 between EN3835 and placebo and their corresponding 95% CIs will be reported.

The FFI pain subscales, and their changes from Baseline will be summarized by study visit (if applicable) and treatment group using appropriate descriptive statistics.

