3.8.1. Foot Function Index

A Foot Function Index (FFI) was developed to measure the impact of foot pathology on function in terms of pain, disability and difficulty limitation. The participant will complete the scale prior to evaluation by the investigator.

The Foot Function Index (FFI) scale for use in Study EN3835-105 was an adapted from the Foot Function Index-Short Form-23(FFI-SF-23) for use in plantar fibromatosis. The FFI-SF-23 is a total foot function assessment instrument (2) (3) comprising 23 items used to assess foot pain, disability, and difficulty in participants with ankle and foot disorders.

Concept elicitation and cognitive interviews were conducted with participants with plantar fibromatosis (n=19) using the FFI-SF-23 to confirm content validity and to confirm that the measure was understandable and relevant in this population. The feedback from the interviews, in combination with FDA feedback resulted in minor revisions to the instrument, which produced a 21-item version, the FFI-PF-May 2021, referred to as the FFI, which will be used in this study. This pain subscale of the FFI will be used in this study in the assessment of the primary endpoint. Additional cognitive interviews (n=7) were conducted, focused specifically on the changes present in the FFI, to confirm content validity and comprehension of the FFI. Based on the second round of cognitive interviews, participants felt that the FFI applied to them and did not recommend changes to the items or response options, therefore no additional changes were made to the FFI.

At the time points included in the SoA (Table 2), each participant will be asked to complete the FFI scale. The participant will complete the scale prior to evaluation by the investigator.

The FFI will be used in this study to assess the impact of EN3835 or placebo on PF. This assessment will be completed at the Screening Visit, Treatment 1 (Day 1), Follow-up Visits (Days 15, 29, and 43) and EOS Visit (Day 57). Each item will be scored on a 5-point verbal rating scale; higher scores are indicative of greater impairment. The FFI comprises 3 subscales as follows:

- Activity limitation subscale (3 items) with a total score of 12: Each response ranges from 0 (“Never”) to 4 (“Always”).
- Difficulty subscale (9 items) with a total score of 36: Each response ranges from 0 (“No Difficulty”) to 4 (“A lot of difficulty”).

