6.2. Derived Variables

Table 25 defines the derived variables for study parameters:

Table 25: Derived Variables and Definition

Variable	Definition
Height (cm)	If height is recorded in inches, then height is equal to the recorded value multiplied by 2.54 and then rounded to 1 decimal place.
Weight (kg)	If weight is recorded in pounds, then weight is equal to the recorded value multiplied by 0.454 and then rounded to 1 decimal place.
Body Mass Index (BMI)	BMI will be computed using height measured at screening and body weight measured at respective visits as, $BMI (kg/m^2) = Weight (kg) / Height (m^2)$
Relative Day	The day of first injection of study intervention will be considered as relative Day 1.
Study Day	Study Day will be computed as, Date of Assessment – Date of Day 1 + 1 for assessment on or after Day 1, else study day will be computed as Date of Assessment – Date of Day 1.
Baseline	Baseline is defined as the last non-missing measurement/assessment prior to the first dose of study intervention. The assessments made in unscheduled visits will be considered in calculation of baseline, if the unscheduled assessment is the closest value preceding the study intervention injection.
Change from Baseline	Change from baseline will be derived as, post-baseline visit/time point value – the baseline value.
Last Date in Study	Last date in study is defined as: 
 • The date of EOS Visit (Day 57 ± 5), if the participant completes the study. • The date of early termination visits if the participant is terminated early from study at a non-scheduled visit. • The date of the latest scheduled visit if the participant is terminated early from study at a scheduled visit or lost to follow-up.
Duration (Days) of AE	AE end date - AE start date + 1
AE Onset Day	AE start date - Date of Day 1 + 1
Total Number of Nodules	Sum of all Nodules Identifier entered in Selected Nodule(s) form
Maximum of Nodule size (mm) (Caliper measurement) for participant level	Maximum of nodule size for the participant
Average Nodular Hardness (Durometer measurement) for Nodule level & Participant level	Average of nodule hardness
Area of the Nodule	$(Nodule\ Width * Nodule\ Length * \pi) / 4$ where $\pi = 22/7$
Area of Nodule for Participant level	Average of nodule area of all nodules

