 - Early withdrawal from the study is the potential intercurrent event that could occur. If participants do not have nodular hardness at Day 57 due to early withdrawal, the missing values will be imputed before the analyses using a multiple imputation washout model. In multiple imputation washout model, all participants who are randomized and have a baseline assessment will be considered (Section 7.6.1.2 for details on imputation).
- **Population Level-Summary measure:** Least square mean (LSM) estimate for treatment difference between EN3835 and placebo.
- **Method of Analyses:** The change from baseline (Day 1) to Day 57 in nodular hardness will be calculated after the missing data imputation has been performed and will be analyzed using ANCOVA model on each imputed dataset. The model will

include the fixed effect of treatment group and average nodular hardness at baseline, the maximum of Nodule length/Nodule width, and the total number of nodules as covariates. Treatment effects from these ANCOVA analyses will then be combined using Rubin's Method via the SAS PROC MIANALYZE procedure. The LSM estimate for each treatment, the LSM of treatment difference, their corresponding 95% confidence interval (CI) and associated p-value will be provided (Section 7.6.1.2 for more details on this analyses).

- **Sensitivity analyses to secondary endpoint:** Following sensitivity analyses will be performed on secondary efficacy endpoint to assess the impact of missing data:
 - A sensitivity analyses will be performed based all observed data up to Day 57. The change from baseline (Day 1) to Day 57 will be analyzed using a MMRM (Section 7.6.1.3).
 - Another sensitivity analyses will be performed using MMRM with imputation of missing values for participant who discontinue treatment or who are withdrawn from the study. The imputed missing values will be adjusted using a TPA (Section 7.6.2).
- **Supportive analyses to secondary endpoint:** The secondary efficacy endpoint will also be analyzed using ANCOVA by FAS and mITT population..

The descriptive statistics for observed and change from baseline at each visit of the hardness measurements (as measured by durometer) by treatment group will be provided for participant level and nodule level.

A listing of nodular hardness by participant will be provided.

7.6.3.3.2. Nodule Level Analyses:

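### The primary and continuous key secondary ANCOVAs are valid but adjust for only one pre-treatment value of the outcome; adding the Screening value is an optional, almost free gain in precision

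*SAP*

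**What the plan says.** SAP 7.6.1.1 analyses change from Day 1 to Day 57 in the FFI pain total with treatment as a fixed effect and "FFI pain subscale score at baseline, the maximum of Nodule length/Nodule width, and the total number of nodules as covariates". Protocol 10.3.1.1.2 gives the same list: "treatment group as fixed effect, FFI pain subscale at baseline, the nodule size and the number of nodules as covariates". SAP 7.6.3.1 (key secondary 1) substitutes the baseline pain plus difficulty score. SAP 7.6.3.3.1 (key secondary 3) uses "average nodular hardness at baseline, the maximum of Nodule length/Nodule width, and the total number of nodules as covariates".

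Baseline is a single value. SAP 6.2, Table 25: "Baseline is defined as the last non-missing measurement/assessment prior to the first dose of study intervention". That is normally Day 1, and Screening only if Day 1 is missing.

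The same measures are scheduled earlier as well. For the FFI, SAP 3.8.1 says "This assessment will be completed at the Screening Visit, Treatment 1 (Day 1", then lists the later visits. The Schedule of Assessments (Protocol 2.3, SAP Table 2) and SAP 3.3 place both the FFI and the durometer reading at Screening and at Day 1 before treatment. None of the three ANCOVA covariate lists includes the Screening value.

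The imputation steps (SAP 7.6.1.2) and the MMRM terms (SAP 7.6.1.3) are redacted. Protocol 10.3.1.1.2 names only the baseline score, nodule size and number of nodules for the MMRM.

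**The concern.** One past-week pain score, or one hand-held hardness reading, measures a participant's usual level with error. A second pre-treatment reading of the same quantity can reduce that error. Both readings precede treatment, so using both as covariates changes neither the estimand nor the definition of change from Day 1. If the second reading carries information beyond the first, omitting it leaves the residual variance larger, and the intervals wider, than the collected data require.

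Precision matters somewhat more than usual here. Planned power is 85%, and SAP 6.5 tests in a fixed sequence, so a near miss on the primary endpoint or on key secondary 1 ends formal testing of everything below it.

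**Working it through.** **1. The plan's own figure.** Protocol 10.1 assumes a difference "between EN3835 and placebo of 5.0 with a 10 standard deviation and 85% statistical power", two-sided 5%. The two-sample t-test needs 72.8, so 73 per arm (146). The normal approximation gives 72 per arm, and 85.6% power at 73. For dropout, 146 / (1 − 0.15) = 171.8, so 172, and 73 / 0.85 = 85.9, so 86 per arm. This agrees with "Assuming a dropout rate of 15%, the total sample size will be 172, eighty-six per treatment group for the study". The sample size reproduces.

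**2. Inputs the documents do not give.** No correlations among Screening, Day 1 and Day 57 are stated. Everything below is conditional on assumed values.

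**3. Both readings equally informative, no selection (relevant to hardness).** Let ρ be the correlation of Screening with Day 1, and λ the correlation of Day 57 with the participant's underlying level. The residual variance with both values, divided by that with Day 1 only, is

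[1 − 2λ²ρ/(1+ρ)] / [1 − λ²ρ].

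- λ = 0.4, ρ = 0.8: (1 − 0.1422) / (1 − 0.128) = 0.984, a cut of about 2%.
- λ = 0.7, ρ = 0.5: (1 − 0.3267) / (1 − 0.245) = 0.892, a cut of about 11%.
- λ = 0.8, ρ = 0.5: (1 − 0.4267) / (1 − 0.32) = 0.843, a cut of about 16%.

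**4. The same with the FFI entry threshold (relevant to the primary endpoint).** Inclusion criterion 3 requires at least 50% on the pain subscale, and Protocol 6.4 requires eligibility at Screening and at Day 1. A simulation with scores of mean 20 and SD 6, rounded to 0–36, both pre-treatment scores at least 18, λ 0.4 to 0.7 and ρ 0.5 to 0.8 gives ratios of 0.987 down to 0.932: cuts of 1.3% to 6.8%. Mean 20 and SD 6 are also assumptions.

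**5. Screening less informative than Day 1.** Screening may fall up to 28 days before Day 1. With a = r(Screening, Day 1), b = r(Day 1, Day 57) and c = r(Screening, Day 57), the ratio is (1 − R²)/(1 − b²), where R² = (b² + c² − 2abc)/(1 − a²). Take a = 0.7 and b = 0.5:

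| c | Ratio, no selection | Cut, no selection | Cut with both scores ≥ 18 |
|---|---|---|---|
| 0.45 | 0.974 | 2.6% | 1.9% |
| 0.40 | 0.994 | 0.6% | 0.5% |
| 0.35 (= ab) | 1.000 | 0% | 0.0% |

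The lower end of the range is therefore 0%.

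**6. Into power.** Take SD 10 as the residual SD after Day 1 adjustment, 73 per arm, normal approximation.

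- Ratio 1.000: SE = 10√(2/73) = 1.655; 5/1.655 − 1.96 = 1.061; power 85.6%.
- Ratio 0.932: SD = 10√0.932 = 9.65; SE = 1.598; 5/1.598 − 1.96 = 1.169; power 87.9%.

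The gain is 0 to about 2.3 points.

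**7. Cost.** The planned model estimates five coefficients, leaving 172 − 5 = 167 residual degrees of freedom. The extra covariate uses one, roughly 1/167 = 0.6% in variance terms. At the bottom of the range the change about breaks even.

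**The case against.** The case against making anything of this is strong, and most of it stands.

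- The planned ANCOVA is valid and already adjusts for baseline, nodule size and nodule number.
- The gain may be nil. Screening may predict Day 57 less well than Day 1 does. At the other extreme, Screening may fall on Day −1, and since the FFI recalls the past week the two recall periods can overlap.
- Selection on the 50% threshold reduces the gain for pain: at most 6.8% with it against about 11% without it.
- The larger figures apply only to hardness, the last endpoint in the testing order.
- A second reading is not guaranteed. Eligibility requires an FFI score but no durometer value. A nodule first recorded on Day 1 has no Screening hardness. Rescreened participants may have two Screening values or may not repeat an assessment (Protocol 6.4).
- Where Screening already serves as baseline, the two covariates coincide. Without a rule, a missing covariate could drop ITT participants.

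Three stronger readings might be inferred. One is that the analysis is wrong or the trial underpowered. The documents do not support this: the sample size reproduces, and Protocol 10.1 does not say whether SD 10 is already covariate-adjusted. If it is the SD of the change score, power at 73 per arm with Day 1 alone is already 90.6% to 96.3% under equal correlations of 0.7 to 0.3. The second is a gain of 11% to 17% on the primary endpoint, which is what equal correlations of 0.5 to 0.7 imply, but that ignores the entry threshold. The third is that Screening is ignored throughout the SAP; the redactions in 7.6.1.2 and 7.6.1.3 prevent that conclusion.

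What survives is narrow: the ANCOVA covariate lists are unredacted and omit a scheduled pre-treatment measure whose inclusion costs about one degree of freedom.

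**Conclusion.** The point holds as an optional improvement. Under the assumptions shown, adding Screening cuts primary residual variance by 0% to about 7%, worth roughly 0 to 2.3 power points at 73 per arm. For hardness the cut is 0% to about 11%, or 16% under the most favourable assumption. No separate figure was worked for the combined pain and difficulty score. These sizes rest wholly on assumed correlations and, for power, on reading SD 10 as the Day 1-adjusted residual SD. That the Screening value is absent from the visible ANCOVA lists is certain; how much it would help is not. No conclusion of the trial would be wrong if the plan stayed as it is.

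**What to change.** Before unblinding, in SAP 7.6.1.1, 7.6.3.1 and 7.6.3.3.1, add the Screening value of the same measure as a second covariate beside baseline: FFI pain total, pain plus difficulty total, and average hardness of the treated nodules respectively. Keep change from Day 1 as the outcome. Record the departure from the covariate list in Protocol 10.3.1.1.2 in SAP Table 28.

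State a rule that keeps every ITT participant in the model:

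- If a Screening value is missing (for example, hardness of a nodule first recorded on Day 1), or Screening already serves as baseline because Day 1 is missing, use the single available pre-dose value for both covariates.
- For rescreened participants, use the latest Screening value.

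Carry the second covariate into the washout imputation model and the corresponding MMRMs if the redacted steps do not already include it.

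The cost is SAP wording, one Table 28 entry, modest programming changes and one residual degree of freedom. No new data or visits are needed.
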